10.5 Statistical considerations

The key exploratory HRQoL endpoint relevant for this study is the global health/QoL scale. The following sub-scales and single items will be considered as supportive exploratory HRQoL endpoints: pain, fatigue, appetite loss, shortness of breath, cough, chest pain and dyspnea symptom scales. The other available scales will be classified as "other" exploratory analyses; the financial difficulties scale will not be presented.

The global health/QoL scale will be used as primary outcome of interest for this study. A difference of 10 points on the 100-point QLQ-C30 scale either within a patient or between the two arms will be considered as clinically relevant [Ref. 78]. The standard deviation of this scale is approximately 20 points. With the 2-sided alpha set at 5% and a power of 80% to detect a difference of 10 points (effect size of 0.5), a minimum of 128 patients (64 per treatment arm) is required. For an effect size of 0.75 (difference of 15 points), 56 patients (28 per treatment arm) are required. Therefore, this study is sufficiently powered to detect differences in HRQoL.

Data will be scored according to the algorithm described in the EORTC scoring manual. All scales and single items are scored on categorical scales and linearly converted to 0-100 scales.

Changes in HRQoL scores from baseline per time point will be evaluated by classifying them according to the 10 point change threshold into 3 categories: improved/stable/deteriorated. Patients without a valid HRQoL outcome at a certain time will be considered as having deteriorated at that time. For each patient the proportion of assessments spent in a deteriorated state will be calculated and compared between treatment arms using a non-parametric rank order test in the intent-to-treat population of the whole population and in the PD-L1 strong positive subgroup.

In order to assess the robustness of the results, the following sensitivity analyses will be performed:

- ◆ a clinical relevant threshold of 5 and 15 points will be used and patients without a valid HRQoL score will be classified according to the reported reason for non-compliance.
- ◆ If adequate compliance available, patients will be classified on valid HRQoL score received after treatment discontinuation only.
- ◆ The area-under-the-curve (AUC) will be calculated for each patient based on the global health/QoL scores. Missing values will be considered as 0.
- ◆ The change from baseline per time point will be displayed graphically.

These analyses will be repeated on the secondary HRQoL scales.

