10.2 Objective

In the present study, HRQoL is a pre-specified exploratory endpoint. The working hypothesis is that pembrolizumab will result in improved DFS compared to placebo with no significant decrement in HRQoL. It is expected that overall self-reported quality of life should be improved due to the improved tumor control but may be affected by immunotherapy related side-effects (fatigue, nausea, pruritus, diarrhea and rash). In addition, the impact of self-reported common symptoms are of interest.

Therefore, overall HRQoL rating and selected symptoms (pain, fatigue, appetite loss, cough, chest pain and dyspnea) will be of interest for the duration of the treatment and for a limited follow-up period afterwards.

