10.4.1 HRQoL schedule

The time windows for eligible HRQoL including EQ-5D assessments will be as follows:

Assessment	Time window
Baseline	Can be completed before or on the day of randomization itself but no earlier than 12 weeks before.
Week 12	Can be completed at week 12 (+/-3 weeks) after randomization.
Week 24	Can be completed at week 24 (+/-3 weeks) after randomization.
Week 36	Can be completed at week 36 (+/-3 weeks) after randomization.
Week 48	Can be completed at week 48 (+/-3 weeks) after randomization.
Week 74	Can be completed at week 74 (+/-4 weeks) after randomization.
Week 100	Can be completed at week 100 (+/-4 weeks) after randomization.
Week 152	Can be completed at week 152 (+/-4 weeks) after randomization.
Week 204	Can be completed at week 204 (+/-4 weeks) after randomization.
Week 256	Can be completed at week 256 (+/-4 weeks) after randomization.

 HRQoL data must be collected regardless of the patient's progression status.

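### The main HRQoL comparison has no time window and, read literally, scores visits missed through death as deteriorated, so a survival benefit can offset a decrement in the treatment year, and no planned between-arm test isolates that year

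*Combined protocol and SAP*

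**What the plan says.** Section 10.2 of the combined protocol and SAP gives the working hypothesis: better DFS without a significant HRQoL decrement. It expects a gain from tumour control and a possible loss from immunotherapy side effects. It says that overall HRQoL and selected symptoms "will be of interest for the duration of the treatment and for a limited follow-up period afterwards".

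Section 10.4.1 sets nine post-baseline assessments: weeks 12, 24, 36, 48, 74, 100, 152, 204 and 256. The last entry reads "Can be completed at week 256 (+/-4 weeks) after randomization".

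Section 10.5 classifies change from baseline at each time point as improved, stable or deteriorated, and treats a patient with no valid outcome at a time as deteriorated at that time. The main test follows: "For each patient the proportion of assessments spent in a deteriorated state will be calculated and compared between treatment arms". It is a rank test in the ITT population, run in the whole population and in the PD-L1 strong positive subgroup.

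The only sensitivity analysis restricted to a period is one in which "patients will be classified on valid HRQoL score received after treatment discontinuation only". The others vary the threshold and classify absent scores by reason for non-compliance, compute an AUC with missing values set to 0, and plot change per time point.

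**The concern.** Treatment is 18 infusions every 3 weeks (Section 5.4), so on schedule the last falls at week 3 x 17 = 51. Four of the nine assessments fall in the treatment year. The last comes 256 - 51 = 205 weeks later, about 3.9 years, which is hard to call limited follow-up.

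Two things then happen to a decrement confined to the treatment year. It is diluted, because it enters four terms of nine. It is also offset, because a patient who has died has no valid score and so counts as deteriorated at every later visit. If pembrolizumab prolongs survival as the design assumes, placebo patients collect more of these visits. The summary becomes partly a survival comparison, with the offset largest where the survival benefit is largest.

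At stake is how a finding of no HRQoL decrement is read. It could arise partly from efficacy while disease-free patients felt worse during their year of adjuvant treatment.

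**Working it through.** **The plan's own figure.** Section 10.5 states "The standard deviation of this scale is approximately 20 points" and, for 10 points at two-sided 5% and 80% power, "a minimum of 128 patients (64 per treatment arm) is required". The normal approximation gives n per arm = 2(1.960 + 0.842)^2 / 0.5^2 = 62.8; the t-test gives 63.8, so 64. For 15 points, "56 patients (28 per treatment arm) are required"; the normal approximation gives 2(2.802)^2 / 0.75^2 = 27.9, so 28. The figures reproduce, but they concern a difference in mean score. They say nothing about the power of a proportion pooled over nine visits.

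**Inputs from the documents.** Visit weeks: Section 10.4.1. OS hazard ratios of 0.765 (whole population) and 0.6 (PD-L1 strong positive): Protocol summary. Accrual: Table 7, which sums to 8 x 8.375 + 18 x 18 + 21 x 34.24 + 5 x 13.992 = 1180 over 52 months.

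**Assumptions, not in the documents.** Exponential survival; 5-year placebo OS of 60-70%; 25-30% of living patients deteriorated at each visit; all survivors return forms; the HRQoL excess on pembrolizumab present at weeks 12-48 only.

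**Formula.** At each visit, P(deteriorated or dead) = 1 - S(t)(1 - d), averaged over the visits counted. Differences are pembrolizumab minus placebo in percentage points; positive means worse on pembrolizumab.

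**Worked case:** 5-year placebo OS 65%, HR 0.765, d = 27.5%, true 5-point excess. Weekly placebo hazard = -ln(0.65)/(5 x 52.18) = 0.00165.

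| Week | S placebo | S pembrolizumab | Difference |
|---|---|---|---|
| 12 | 0.980 | 0.985 | +4.6 |
| 24 | 0.961 | 0.970 | +4.2 |
| 36 | 0.942 | 0.956 | +3.8 |
| 48 | 0.924 | 0.941 | +3.5 |
| 74 | 0.885 | 0.911 | -1.9 |
| 100 | 0.848 | 0.881 | -2.4 |
| 152 | 0.778 | 0.825 | -3.4 |
| 204 | 0.714 | 0.773 | -4.3 |
| 256 | 0.655 | 0.724 | -5.0 |

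Mean over weeks 12-48: +4.0. Mean over weeks 74-256: -3.4. Pooled: (4 x 4.01 - 5 x 3.39)/9 = -0.1. With no true HRQoL difference the pooled value is -2.2. So dilution reduces the 5 points to about 2.1, and deaths remove the rest.

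**Range over the assumptions, all nine visits due, HR 0.765.**
- No true excess: pooled -1.9 to -2.6.
- 5-point excess: +3.8 to +4.2 over weeks 12-48; -0.5 to +0.3 pooled.
- 10-point excess: +8.6 to +9.0 over weeks 12-48; about +1.6 to +2.4 pooled.

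**HR 0.6, same formula.** A 5-point excess is -2.5 to -1.1 pooled; a 10-point excess is -0.3 to +1.1.

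**Dependence on cut-off.** For each month of entry, average the differences over visits due by the cut-off, then weight by the Table 7 accrual (d = 27.5%, HR 0.765).
- Month 60: about 1% of patients have all nine visits due; a 5-point excess shows as +1.9 to +2.4, a 10-point excess as +5.3 to +5.8.
- Month 72: about 13% have all nine due; +0.9 to about +1.4, and +3.7 to +4.3.
- Everyone has all nine due only from about month 52 + 256/4.348 = 111.

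**Effect on the test.** Simulation used 590 per arm, a two-sided 5% Mann-Whitney test, 5-year placebo OS 65%, HR 0.765, 10% of forms missing, a patient random effect, and 30% deteriorated after treatment in both arms. With 33% versus 25% deteriorated on treatment, a significant result against pembrolizumab appears in 94% of trials over weeks 12-48 and 9% over all nine visits. Pooling only visits while alive gives 68%. How death is scored therefore costs more than dilution does.

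**The case against.** The strongest reply is that Section 10.2 asks a net question. It expects improvement through tumour control as well as possible harm from side effects, and it names a follow-up period. A reader might infer that an on-treatment decrement is the plan's sole HRQoL question; the text does not support that. Choosing a net or an on-treatment estimand is partly a design judgement, so weeks 12-48 need not simply replace the main comparison.

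A reader might also infer that the five later visits say nothing about tolerability. Appendix G says immune-related events may occur several months after the last dose, and Section 5.5 lets delayed treatment run past one year. Week 74 at least, and plausibly week 100, can carry such information.

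Nor does Section 10.5 say outright that deaths count as deteriorated, or that all nine visits form the denominator. Both follow from the literal wording, and the sponsor may intend otherwise. If so, the plan should say so.

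There are partial mitigations. Change is classified and plotted by time point, absent scores are reclassified by reason in a sensitivity analysis, and Section 10.5.2 allows a longitudinal model. An on-treatment decrement might well be visible in the plots. What stands is that none of these commits to a between-arm test of the treatment period, and the AUC with missing values set to 0 carries the same problem as the main analysis.

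**Conclusion.** The concern holds as a gap in the specification with a predictable direction: as written, the main summary mixes HRQoL with survival and extends well past the period Section 10.2 describes. Under the stated assumptions at HR 0.765, a 5-point excess worth 3.8 to 4.2 points over weeks 12-48 falls to about +0.9 to +2.4 at a month-60 to month-72 cut-off and to about -0.5 to +0.3 at full follow-up. The offset is larger at HR 0.6.

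A reader might conclude that the decrement is cancelled whenever the analysis is run. That is the long-follow-up case; earlier cut-offs mainly attenuate, and at HR 0.765 a 10-point excess is reduced but not removed even with all nine visits due. The sizes rest on placebo survival and deterioration rates that the documents do not show, and on reading the missing-score rule as covering death. HRQoL is exploratory, so no primary or key secondary conclusion is affected; what changes is what can be said about HRQoL during treatment.

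**What to change.** In Section 10.5:

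1. Pre-specify a between-arm comparison of the proportion of assessments deteriorated over weeks 12, 24, 36 and 48, optionally with a stated short follow-up such as week 74 to match Section 10.2. Report it alongside or ahead of the pooled proportion.
2. Report the later visits separately, with death as its own category and not as HRQoL deterioration.
3. Exclude from the denominator any visit not yet due at the data cut-off.
4. Keep the nine-visit proportion as supportive.

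The cost is SAP wording and one extra run on data already being collected.

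### The quality-of-life plan hypothesises no decrement but tests only for a difference and applies no margin, so a non-significant result cannot support preservation

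*Combined protocol and SAP*

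**What the plan says.** Section 10.2 gives the aim: "The working hypothesis is that pembrolizumab will result in improved DFS compared to placebo with no significant decrement in HRQoL". The same section adds that overall quality of life is expected to improve through tumour control but may be affected by immunotherapy side-effects. It also fixes the status: "In the present study, HRQoL is a pre-specified exploratory endpoint".

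Section 10.5 makes global health/QoL the key scale and treats 10 points, within a patient or between arms, as clinically relevant. It then gives a sample-size statement: "The standard deviation of this scale is approximately 20 points", and for 10 points at two-sided 5% and 80% power "a minimum of 128 patients (64 per treatment arm) is required". It concludes: "Therefore, this study is sufficiently powered to detect differences in HRQoL".

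The main analysis uses a different variable. Each visit is classed as improved, stable or deteriorated by a 10-point change from baseline, and a visit without a valid score counts as deteriorated. Then "the proportion of assessments spent in a deteriorated state will be calculated and compared between treatment arms using a non-parametric rank order test", in the whole ITT population and in the PD-L1 strong positive subgroup.

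**The concern.** The hypothesis is about preservation, and the analysis is a test for a difference. Failing to find a difference is not evidence that there is none. The 10-point figure that could act as a margin is used in the main analysis only to classify change within a patient, never to judge a difference between arms.

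The planned sensitivity analyses are 5- and 15-point thresholds, reclassification of missing visits by reason, post-discontinuation scores, AUC with missing set to 0, and plots of change. None adds an interval or a decision rule. The longitudinal model in section 10.5.2 is optional and addresses deterioration linked to progression.

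Counting missing as deteriorated adds a second difficulty. The rank test compares a mixture of score loss and missingness, so the two can offset each other. At stake is a supportive statement that adjuvant pembrolizumab does not cost patients quality of life. As written, that statement could rest on a p-value above 0.05.

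**Working it through.** **Inputs from the documents.** SD 20; relevant difference 10 points; two-sided 5%; 80% power (section 10.5). About 590 per arm (section 4.1.3). About 334 strong positive patients, so 167 per arm (protocol summary). Nine post-baseline assessments, weeks 12 to 256 (section 10.4.1). The documents give no missing-data rate, within-patient correlation or expected share of deteriorated visits for quality of life. Those are assumptions below.

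**1. The plan's own figure.** A two-sample t-test with effect size 10/20 = 0.5 needs 63.8, so 64 per arm: the stated 128 reproduces. For 15 points the normal approximation gives the stated 28 per arm (the t-test gives 29). The statement therefore describes a comparison of two mean scores. No power is given for the rank test.

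**2. The rank test when missingness is equal.** Simulation with nine visits, SD 20, within-patient correlation 0.5 to 0.7, missing counted as deteriorated and missingness clustered within patients (600 to 1,000 runs each):

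| Per arm | True decrement | 0% missing | 30% missing | 50% missing |
|---|---|---|---|---|
| 64 | 10 | 94–99% | 70–88% | 48–71% |
| 167 | 10 | 100% | 98–100% | 90–98% |
| 167 | 5 | 80–95% | 51–64% | 32–44% |
| 590 | 5 | 100% | 97–100% | 79–92% |

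So 64 per arm does not fix 80% power for this measure. At the trial's real sizes, a 10-point decrement is detected with high power.

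**3. The rank test when missingness differs.** With correlation 0.5, the SD of a change score is 20 × √(2 × (1 − 0.5)) = 20. The chance of a drop of at least 10 points is:

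- no true change: Φ(−10/20) = Φ(−0.50) = 0.309
- true 5-point decrement: Φ(−5/20) = Φ(−0.25) = 0.401

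With missing share m, the share of visits classed as deteriorated is m + (1 − m)p:

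- placebo, m = 0.40: 0.40 + 0.60 × 0.309 = 0.585
- pembrolizumab, m = 0.30: 0.30 + 0.70 × 0.401 = 0.581

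The two are almost equal. Simulated rejection is 3.3% with 167 per arm and 5.5% with 590, which is about the test's error rate when nothing differs. A larger sample does not help.

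**4. What an interval would give.** The half-width for a difference in means is 1.96 × 20 × √(2/n):

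- n = 590: 2.28 points; n = 167: 4.29 points
- with half the patients evaluable, n = 295: 3.23 points; n = 84: 6.05 points

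With a true difference of 0, a 10-point margin at one-sided 2.5% needs 63 per arm (80% power) or 85 (90%). A 5-point margin needs 252 or 337. That is available in the whole population but not with 167 per arm, where power is Φ(5/2.19 − 1.96) = 63%.

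**The case against.** The best defence is that the endpoint is exploratory and outside the type I error control, which covers DFS and OS. The plan also expects movement in either direction, so a test for a difference is coherent. No formal non-inferiority claim is made, and counting missing as deteriorated is a deliberate, conservative choice in a setting where section 10.5.1 names missing data as a major source of bias. All of this stands. It limits the consequence and is a reason to keep the planned test, but it does not make non-significance evidence for the hypothesis in section 10.2.

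A reader might infer three stronger things that the documents do not support.

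- *That the trial is underpowered for quality of life.* It is not for 10 points: step 2 gives 90–98% with 167 per arm and half the assessments missing. The shortfall appears at 64 per arm, a size the trial does not use.
- *That t-test figures describe the planned test.* On mean scores, 167 per arm would miss a 5-point decrement about 38% of the time. With complete data the rank test misses it about 5–20% of the time.
- *That no outcome could speak to preservation.* A significant rank test favouring pembrolizumab would argue against a decrement on that measure. The gap concerns the non-significant result.

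The −10 rule also has a cost. Under a true 5-point loss it would still declare no clinically relevant decrement with probability Φ(5/2.19 − 1.96) = 63% at 167 per arm and Φ(5/1.16 − 1.96) = 99% at 590. That follows from the plan's own view of what is relevant, and is why a −5 reading belongs beside it.

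**Conclusion.** The point holds in limited form. Chapter 10 hypothesises no decrement, but it supplies neither an interval for an arm difference nor a rule for concluding preservation, and its power statement describes a different analysis. A non-significant rank test cannot support the hypothesis. In the illustrated case a true 5-point decrement is flagged about 5% of the time at any sample size the trial has.

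That illustration rests on assumed random missingness of 40% on placebo and 30% on pembrolizumab, SD 20 and correlation 0.5. The direction is plausible if DFS improves, but the documents give no rate and the imbalance could run the other way. The sample size is adequate for a 10-point question in both populations. The primary conclusions are untouched.

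**What to change.** - Keep the rank test with missing counted as deteriorated, and state that its non-significance will not be read as preserved quality of life.
- Add a pre-specified between-arm difference in mean change from baseline in global health/QoL over the scheduled visits. Adjust it for baseline score and the minimisation factors, and report a 95% confidence interval in the whole population and in the strong positive subgroup.
- State that there is no clinically relevant decrement only if the lower limit lies above −10, the plan's own threshold. Report −5 as a sensitivity margin, noting that it is underpowered in the strong positive subgroup.
- Relabel the 128-patient statement as applying to that mean difference.

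The cost is some SAP wording and one standard model on data already being collected. The downside is that the added model assumes data missing at random, so its result must be read beside the missing-as-deteriorated analysis and not in place of it.

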8.1.2 Randomization and stratifications

All patients entered will be centrally registered at the EORTC Headquarters (for practical details, see Chapter on randomization procedure). The Pocock and Simon Minimization with Biased-coin Assignment methodology [Ref. 73] will be utilized to perform subject randomization for this study. Per suggestion of the ICH E9 statistical guidelines, the algorithm has been modified to incorporate a random allocation component in order to ensure 15% of completely random assignments. Stratification factors are: stage (IB vs II vs IIIA), adjuvant chemotherapy (no adjuvant chemotherapy versus adjuvant chemotherapy), PD-L1 status: negative (TPS=0%) versus weak positive (TPS = 1-49%) - versus strong positive (TPS≥50%) and regions (Western Europe versus Eastern Europe versus Rest of the world versus Asia). Minimization algorithm separately applied for each PD-L1 status, to ensure an optimal balance of treatment arms within each PD-L1 level.

Treatment allocation will be blinded (see Chapter 14).

Note: Tumor staging is based on TNM stage (according to the 7th edition of the TNM classification for lung cancer).

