8.2.3 Statistical methods

8.2.3.1 Efficacy endpoints

The primary analyses of the primary and secondary efficacy endpoints (DFS, OS and LCSS) will be performed on all randomized patients according to the intention to treat (ITT) principle.

Estimates and confidence intervals

Estimates of the median DFS, OS and LCSS will be obtained by the Kaplan Meier technique. The 95% confidence interval (CI) for the median will be calculated using the reflected CI method.

Estimates of the event-free rate at a fixed time point will be obtained using the Kaplan Meier technique and 95% CI will be calculated by the Greenwood's formula for standard deviation. Estimates of hazard ratios and their 95% CI will be obtained by Cox regression. Kaplan Meier curves will be drawn for both the experimental and control arms on the same plot.

Inference

The DFS and OS will be analyzed by a Cox Proportional Hazard Regression with treatment adjusted by the following covariates: stratification factors including stage, PD-L1 IHC expression, adjuvant chemo, regions, and additional factors including histology and smoking status. Permutation test [Ref. 74] will be used as a primary test for DFS to compare the experimental versus the control arm. The Wald test without permutation of allocation sequence will be used as a supportive analysis for DFS, but as a primary test for OS. The hazard ratios and corresponding 95% CIs will be estimated using the multivariate Cox regression model stated above (using Efron's tie-handling method). A sensitivity analysis will include sex (male vs. female) and age (<65 vs. ≥ 65 years) as additional adjustment factors in the Cox regression model. A logrank test with no adjustment factors to compare the two arms will also be performed as a sensitivity analysis.

If a randomized patient is not disease free at baseline, the date of randomization will be used as the date of event for the primary DFS analysis in the PD-L1 strong positive, PD-L1 positive and the whole population.

Analysis of LCSS will be based on the log-rank test and Cox regression model. Competing risks approaches such as cumulative incidence function (CIF), Gray's test, Fine-Gray subdistribution hazard model, etc., will also be performed, where deaths from other causes are considered as competing risks. As no Type I error control is applied to LCSS, the p-values for LCSS analyses, if provided, are nominal only and for descriptive purpose.

Table 10. Analysis Strategy for Key Efficacy Variables

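### The main HRQoL rank test specifies no adjustment for the baseline score or the minimisation factors: an avoidable loss of precision for small decrements on an exploratory endpoint

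*Combined protocol and SAP*

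**What the plan says.** Section 10.5 works from change since baseline: "Changes in HRQoL scores from baseline per time point will be evaluated by classifying them according to the 10 point change threshold into 3 categories" (improved, stable, deteriorated). Missing forms count against the patient: "Patients without a valid HRQoL outcome at a certain time will be considered as having deteriorated at that time". Each patient's share of deteriorated assessments is then "compared between treatment arms using a non-parametric rank order test in the intent-to-treat population of the whole population", and the same comparison is made in the PD-L1 strong positive subgroup. The rank test is not identified further, and no covariate or stratum is named. The listed sensitivity analyses (thresholds of 5 and 15 points, post-discontinuation scores, AUC with missing values set to 0, plots) add none.

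The baseline form is due by the day of randomisation. Section 10.4.1 says: "Can be completed before or on the day of randomization itself but no earlier than 12 weeks before". Treatment is allocated by minimisation on stage, adjuvant chemotherapy, PD-L1 and region (8.1.2): "Minimization algorithm separately applied for each PD-L1 status, to ensure an optimal balance of treatment arms within each PD-L1 level". The DFS and OS models in 8.2.3.1 do adjust, for "stratification factors including stage, PD-L1 IHC expression, adjuvant chemo, regions, and additional factors including histology and smoking status".

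Section 10.2 makes HRQoL exploratory, with the working hypothesis that pembrolizumab brings no significant loss of HRQoL.

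**The concern.** The outcome is tied to the baseline score by construction. A patient who starts high has room to fall and tends to regress to the mean. A patient near the bottom of the 0-100 scale cannot lose 10 points. Baseline HRQoL is not a minimisation factor, so only chance balances it between arms, and a test that leaves it out carries that variation as noise.

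The direction matters because the hoped-for answer is no significant decrement, and a less precise test makes that answer easier to reach. The plan's statement that power is sufficient rests on a comparison of two means, not on the rank test that will be run. DFS and OS, under the same randomisation, are adjusted for all four minimisation factors.

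**Working it through.** **Inputs from the plan.** Section 10.5: "The standard deviation of this scale is approximately 20 points"; two-sided 5%; 80% power; relevant difference 10 points. Section 4.1.3: 1180 patients, about 590 per arm. Protocol summary: about 334 PD-L1 strong positive patients, so 167 per arm. Section 10.4.1: nine post-baseline assessments, weeks 12 to 256.

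**Assumptions not in the plan.** Correlation of baseline with follow-up, mean score, share and pattern of missing forms, and prognostic strength of the strata.

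**1. The plan's sample size.** n per arm = 2(1.960 + 0.842)²(SD/difference)². For 10 points: 2 × 7.85 × 4 = 62.8, so 63 per arm (126). For 15 points: 2 × 7.85 × 1.78 = 27.9, so 28 per arm (56). The t-test version gives 64 (128) and 29 (58). The stated 128 and 56 therefore reproduce to within 2 patients. Power at 64 per arm is 80.7%.

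**2. Size of chance imbalance.** SE of the baseline difference = 20√(2/167) = 2.2 points in the subgroup (95% range about ±4.3) and 20√(2/590) = 1.2 points overall (about ±2.3). At correlation 0.5, half of any imbalance appears as a difference in change. It averages to zero over randomisations, so it is noise.

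**3. How much baseline explains.** For one change score with equal variances, R² = (1 - ρ)/2: 0.30, 0.25 and 0.20 at ρ = 0.4, 0.5 and 0.6. Simulating the plan's actual outcome with complete data, baseline explained 19 to 32% of the rank variance. Because missing counts as deteriorated, this fell to 16-18% with about 10% missing, 12-14% with about 19%, and 4-13% with about 27 to 46%.

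**4. From R² to power.** Adjusted power = Φ[(1.96 + z)/√(1 - R²) - 1.96], where z is the normal quantile of the unadjusted power. At unadjusted power of 50 to 70%, R² = 0.20-0.25 gives 9 to 12 points, R² = 0.10 gives 4 to 5, and R² = 0.05 about 2.

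**5. Simulation of the rank test.** SD 20, mean 70, scores on the questionnaire's grid within 0-100, correlation 0.5 with baseline and 0.65 between follow-ups, missing share rising over time, and a four-level stratum with SD about 3 points. Power in %:

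| N | Decrement | Missing | Unadjusted | Baseline | Baseline + stratum | Gain |
|---|---|---|---|---|---|---|
| 1180 | 2 | 0 | 48.9 | 61.3 | 61.5 | 12.6 |
| 1180 | 3 | 0 | 81.8 | 91.6 | 92.2 | 10.4 |
| 1180 | 3 | 10% | 65.2 | 72.3 | 74.2 | 9.0 |
| 1180 | 2.5 | 19% | 38.0 | 40.8 | 42.1 | 4.1 |
| 334 | 4 | 0 | 54.1 | 65.9 | 66.7 | 12.6 |
| 334 | 5 | 0 | 72.5 | 83.7 | 84.8 | 12.3 |
| 334 | 5 | 10% | 56.2 | 65.4 | 66.3 | 10.1 |
| 334 | 5 | 19% | 42.7 | 49.0 | 49.9 | 7.2 |
| 334 | 4 | 27% | 23.3 | 24.3 | 25.8 | 2.5 |
| 334 | 4 | 46% | 17.3 | 18.2 | 19.8 | 2.5 |
| 334 | 10 | 0 | 99.9 | 100.0 | 100.0 | 0.1 |
| 334 | 10 | 19% | 96.6 | 98.0 | 98.4 | 1.8 |

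With no treatment effect, rejection rates were 5.1%, 5.25% and 5.4% for the three tests. Over correlations 0.4 to 0.6, complete data gave gains of about 8 to 18 points at 2-3 points (N=1180), and 27 to 46% missing gave -1 to +9. The stratum added about 0 to 4 points.

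**6. A second, separate simulation.** Mean 65, exchangeable correlation, 15% of forms missing at random, baseline adjustment only. At correlation 0.5: N=334, 5 points, 72.9% to 87.0%; N=334, 4 points, 51.3% to 65.5%; N=1180, 3 points, 81.4% to 91.8%. At N=334 and 5 points, correlation 0.3 gave 56.8% to 82.0% and correlation 0.7 gave 84.1% to 89.6%. With 40% monotone dropout (N=334, 5 points) the change was 45.0% to 51.3%. The pattern of missing forms therefore matters as well as the share.

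**The case against.** The strongest objection is relevance. Section 10.5 sets 10 points as the relevant difference both within a patient and between arms, and there the test loses almost nothing. The 5-point value in the plan is a sensitivity threshold for classifying patients, not a between-arm target. This stands: the gain concerns decrements smaller than the plan set out to detect.

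The gain also rests on a correlation and a missing share that the plan does not give. Section 10.4 itself expects attrition by year 5, and 10.5.1 provides for overall compliance below 50%. The less favourable rows of the table may therefore be the realistic ones. This also stands, and it is why the size is given as a range.

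The endpoint is exploratory, type I error control covers only DFS and OS, and no formal non-inferiority claim depends on this test. That lowers the severity, and it weakens the contrast with the DFS and OS models.

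Two replies are only partial. Section 10.5.2 allows a longitudinal model with treatment, time, selected clinical factors and progression status. It is optional, serves the question of deterioration after progression, and does not name the baseline score. Baseline also enters through the change score, so it is not ignored altogether. But at these correlations change scores remain correlated with baseline, as step 3 shows. Finally, a stratified rank test is not excluded; it is simply not specified.

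**Conclusion.** The point holds as a modest efficiency loss on an exploratory endpoint, of low severity. For decrements of about 2 to 3 points (N=1180) or 4 to 5 points (N=334), adjustment should add roughly 0 to 18 points of power for correlations of 0.4 to 0.6. That is about 10 to 14 at correlation 0.5 with near-complete data, 4 to 10 with 10 to 20% missing scored as deteriorated, and -1 to +9 with more. At the plan's 10-point difference the gain is 0 to 2 (checked at correlation 0.5 with up to about 19% missing). With complete data nearly all of it comes from baseline; the strata add 0 to 4 points.

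A reader might infer more than the documents support:

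- That the comparison is biased or its type I error inflated. It is neither: both tests reject at about 5% under no effect.
- That a fixed 10 to 14 points is lost. That figure needs an assumed correlation and near-complete data.
- That HRQoL is underpowered for its stated target. In the settings checked, the unadjusted test keeps at least 96.6% power at 10 points.
- That the loss is worst in the PD-L1 strong positive subgroup. The gain is the same, about 13 points, at 2 points with N=1180 and 4 points with N=334. It depends on the starting power, not on the subgroup.

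**What to change.** In section 10.5:

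- Name the main between-arm test as a rank ANCOVA: ranks of the per-patient proportion on arm, baseline score, stage, adjuvant chemotherapy, PD-L1 and region. Omit PD-L1 in the strong positive subgroup, where it is constant.
- Because a rank-scale difference is hard to interpret, report alongside it the baseline-adjusted difference in mean proportion of deteriorated assessments, with its 95% CI.
- Adjust the AUC sensitivity analysis for baseline in the same way.
- State how patients without a baseline form are handled, by a missing indicator or a mean-imputed baseline.
- Keep the unadjusted rank test, named, as a sensitivity analysis.

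The cost is SAP wording, the rule for missing baselines and a small amount of programming. Every covariate is already collected. The change should be fixed before unblinded HRQoL data are examined.
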